1.2 Protocol Synopsis

Title	Long-term Outcomes of Children with Hypoplastic Left Heart Syndrome and the Impact of Norwood Shunt Type (SVR III)
Study Objectives	
 1. To determine if shunt type at the time of Norwood operation is associated with long-term differences in cardiac function, survival or contributors to quality of life. 2. To characterize long-term outcomes and determine risk factors other than shunt type for adverse long term outcomes in children with hypoplastic left heart syndrome (HLHS) and other related single ventricle anomalies.
Significance	The proposed long-term follow-up of the Single Ventricle Reconstruction (SVR) trial cohort is required to determine the optimal shunt approach for children with HLHS.
Study Design	Prospective follow-up study of the SVR cohort
Primary Aim	To compare direct and indirect measures of right ventricular (RV) systolic and diastolic function between 11 year old subjects who had been randomly assigned to receive a right ventricle to pulmonary artery shunt (RVPAS) vs. a modified Blalock-Taussig shunt (MBTS) at the time of the Norwood operation.
Secondary Aim(s)	
 1. To compare the incidence of death or cardiac transplantation between those randomized to receive a RVPAS vs. a MBTS at the time of the Norwood operation. 2. To compare exercise tolerance between those randomized to a RVPAS vs. a MBTS. 3. To compare the incidence of arrhythmias between those randomized to a RVPAS vs. a MBTS. 4. To compare neurodevelopmental outcomes at 11 years of age in those randomized to a RVPAS vs. a MBTS 5. To develop risk stratification models for 1) cardiac outcomes, 2) transplant-free survival, and 3) neurodevelopmental outcomes. 6. To collect specimens from subjects and their parents to further develop the biologic specimen repository.
Accrual Objective	Fixed cohort, ideally with a 2 year window for participation (11 \pm 1 year of age), but subjects can be enrolled at any time there is interest in participation up until September 30, 2020.
Study Duration	10.5 years (June 2015 - November 2025)
Inclusion Criteria	Transplant-free survivors of the SVR cohort (All SVR survivors are eligible to be followed for vital status.)
Exclusion Criteria	Participants who received cardiac transplantation or biventricular conversion will be excluded from all outcomes other than vital status.

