- Achievement, as measured by the Wechsler Individual Achievement Tests (WIAT) (Math and Reading)
- Intelligence, as measured by the Wechsler Intelligence Scale for Children (WISC)
- Other domains of neurodevelopmental function including assessment of language, executive function, visual spatial skills, motor function, memory, social skills, behavior, health-related quality of life (HRQoL) and adaptive function.

Secondary Aim 5: To develop risk stratification models for the following classes of long term outcomes: 1) cardiac outcomes, 2) transplant-free survival, and 3) neurodevelopmental outcomes.

Hypothesis: Long-term outcomes at 11 years will be worse for participants with a higher frequency of medical events.

Analyses for this aim will:

- Provide information about the association of events and interventions other than the randomized surgical procedure with late outcomes.
- Identify early cardiac and neurodevelopmental surrogate endpoints that might be useful in future studies of management strategies.
- Determine if correlates of long-term outcomes vary according to patient subgroup factors.

Secondary Aim 6: To collect specimens from subjects with HLHS and other single RV anomalies and their parents in whom DNA samples either were not collected previously or are of insufficient quality or quantity, to further develop the biologic specimen repository (biorepository).

Purpose: *To build on the collection of genetic material from the SVR cohort, to leverage the careful phenotyping of the SVR cohort to provide an opportunity for future phenotype-genotype studies and to make samples available for future hypothesis-driven studies aimed at identifying genetic determinants of outcome in HLHS and related single RV lesions.*

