4.3.3. Covariate Measures

The unique nature of this large inception cohort presents the opportunity to examine events that commonly occur in this population as both risks and outcomes. To that end, a number of events will be collected as covariate measures. Covariates that are available from the SVR trial, SVR II and annual visit forms include:

SVR and SVR II:

- Pre-Stage I: prenatal diagnosis, genetic syndrome, socioeconomic status, birth weight/gestational age, occurrence of neonatal shock.
- Stage I hospitalization: mechanical ventilation time, cardiopulmonary bypass and deep hypothermic circulatory arrest/regional cerebral perfusion times, ICU/hospital length of stay, delayed sternal closure, use of extracorporeal membrane oxygenation (ECMO), unplanned surgical/catheter interventions.
- Interstage, post stage II and post stage III: unplanned surgical/catheter interventions, cardiac arrest, ECMO.
- Stage II/Stage III: mechanical ventilation time, cardiopulmonary bypass and deep hypothermic circulatory arrest/regional cerebral perfusion times, ICU/hospital length of stay, delayed sternal closure, use ECMO, and unplanned surgical/catheter interventions.

Medical history data:

- Treatment with heart failure medications, (angiotensin converting enzyme inhibitors, angiotensin receptor blockers, beta-blockers), treatment for pulmonary hypertension, use of anticoagulants.
- New diagnoses: stroke, plastic bronchitis and protein losing enteropathy will be recorded.
- Weight and height will be measured at the time of the CMR and/or the exercise test.

Procedural history data:

- Unanticipated interventions: catheterization or surgery, (pacemaker implantation, stent implantation, Fontan revision, etc.), use of mechanical circulatory support, and lack of Fontan completion will be noted.

Socioeconomic (SES) data from the SVR and SVR II studies will be included as possible covariates in models for survival and ND outcomes. Educational status of the child, family structure, and language spoken in the home will be collected. In addition, maternal education level and current address information to determine census block variables such as percent within the census block living below the poverty level, will be collected at the time of ND evaluation to allow us to determine and adjust for the contribution of these factors to survival and ND outcomes at 11 years of age.

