5. SELECTION AND WITHDRAWAL OF SUBJECTS

5.1 Subject Inclusion:

All SVR study cohort members will be contacted to assess for vital status. Transplant free survivors will be approached to participate in the in-person assessment.

5.2 Subject Exclusion:

We will exclude patients who have undergone cardiac transplantation or biventricular conversion from all outcomes other than vital status. Those with pacemakers will be excluded from the CMR, and patients unable to comfortably reach the exercise bike pedals enough to effectively pedal the cycle ergometer will be excluded from the exercise test.

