Arrhythmias will be classified as atrial tachyarrhythmias or ventricular tachyarrhythmias. The rate of atrial and of ventricular tachyarrhythmias will be compared between the shunt groups with the Fisher exact test.

7.1.2.e Secondary Aim 4: To compare neurodevelopmental outcomes at 11 years of age in subjects randomized to a RVPAS vs MBTS

Descriptive statistics will be performed for each scale included in the ND battery. Student's t-test will be used to compare normally distributed measures, Wilcoxon Rank-Sum for non-parametric continuous measures and Fisher exact test for all dichotomous measures. Adjustment will be included for measures of socioeconomic status.

7.1.2.f Secondary Aim 5: To determine if early perioperative events other than type of systemic to pulmonary artery shunt are related to long-term outcomes

To determine if early events after the Norwood operation are related to long-term outcomes, comprehensive models will be explored for each of the primary outcome measures for each aim (RVEF by CMR, transplant-free survival at 11 years, VO₂ max at ramped cycle ergometry, incident atrial tachyarrhythmias, incident ventricular tachyarrhythmias, Wechsler full scale IQ, and Language and Math Achievement Tests). Candidate predictors for these models will include previously collected early events and additional medical and surgical variables since the last SVR/SVR II contact.

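### Socioeconomic data collected at the neurodevelopmental visit cannot adjust survival from randomization, and the survival risk models give no risk set or time-dependent rule for later events

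*Combined protocol and SAP*

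**What the plan says.** **Socioeconomic status (SES).** Section 4.3.3 first makes the SES data from SVR and SVR II available to the survival and ND models. It then adds maternal education and census-block variables, which "will be collected at the time of ND evaluation to allow us to determine and adjust for the contribution of these factors to survival" as well as to ND outcomes at 11 years. Under Section 5.1, "Transplant free survivors will be approached to participate in the in-person assessment". The synopsis gives the study duration as "10.5 years (June 2015 - November 2025"), so no such visit can predate June 2015.

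**Later events.** Section 7.1.2.f states that "comprehensive models will be explored for each of the primary outcome measures for each aim (RVEF by CMR, transplant-free survival at 11 years" and other outcomes), and then that "Candidate predictors for these models will include previously collected early events and additional medical and surgical variables since the last SVR/SVR II contact". Section 4.3.3 says the cohort "presents the opportunity to examine events that commonly occur in this population as both risks and outcomes". Its procedural history includes "pacemaker implantation, stent implantation, Fontan revision, etc.), use of mechanical circulatory support, and lack of Fontan completion will be noted". The Aim 5 hypothesis in Section 2.2 is that "Long-term outcomes at 11 years will be worse for participants with a higher frequency of medical events".

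**Time scale.** Section 7.1.2.b counts time to death or transplant from randomization. It plans a Cox model that will also look for risk factors, plus a subdistribution hazards model. Its only time-related element is whether the shunt effect changes over time. The outcome in Section 2.2 that is conditional on surviving the first year belongs to the Aim 1 shunt comparison and sets no rule for covariates. No section specifies a landmark, delayed entry, time-dependent coding, or a limit on which predictors may enter the survival model.

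**The concern.** A predictor of survival from randomization has to be known at randomization, or has to enter the model only from the moment it becomes known. The two kinds of variable here fail that in different ways.

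- **ND-visit SES** exists only for children who lived transplant-free to the visit and attended. Among the rest it is missing because of the outcome, so the usual ways of handling missing covariates do not repair it.
- **Later medical and surgical events** can happen only to children who have survived long enough. Coded as fixed yes/no covariates from time zero, they credit the exposed children with all the event-free time before the event (immortal time), and the event then looks protective.

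Aim 5 is meant to provide risk stratification for transplant-free survival and hypothesizes that more events mean worse outcomes. With fixed coding, the model could contradict that hypothesis when it is true.

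**Working it through.** **1. The plan's own count.** Section 5.4: 352 alive in June 2014, 18 of them transplanted. 352 - 18 = 334, which matches Section 7.2. So 549 - 334 = 215 children (39%) were no longer counted as alive and transplant-free. The documents do not separate deaths from losses to follow-up, so 215 is an upper limit on endpoints.

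**2. Endpoints still to come.** The documents give no 11-year transplant-free survival. Section 7.3 illustrates 50% against 63% at study end; I borrow that range as an assumption (midpoint 56.5%).

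| Assumed 11-year survival | Total losses | After June 2014 |
|---|---|---|
| 50% | 549 x 0.50 = 274.5 | 59.5 |
| 56.5% | 549 x 0.435 = 238.8 | 23.8 |
| 60% | 549 x 0.40 = 219.6 | 4.6 |
| 63% | 549 x 0.37 = 203.1 | none (below 215) |

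At the midpoint, 215 / 238.8 = 90% of endpoints precede June 2014.

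**3. ND-visit SES, complete cases.** Assume a mean age of 7.5 years in June 2014, a constant hazard from there to 11, and 80-90% taking part. At 50% survival the hazard is ln(0.608 / 0.50) / 3.5 = 0.056 per year. Survival at 10 is then 0.50 x exp(0.056) = 0.529, and losses between 10 and 11 are 549 x 0.029, or about 15.8.

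- If every visit is at exactly age 10: 15.8 x 0.8 to 0.9 = 12.7-14.2 endpoints kept.
- If visits are spread evenly over ages 10-12, about a quarter of those losses follow a visit: 3.1-3.5 kept.
- At 56.5% survival the two cases give 5.3-6.0 and 1.3-1.5; at 60%, 1.0-1.2 and 0.3.

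So about 0 to 4, and at most 14, of some 220-275 losses would remain.

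**4. Later events, a hand check.** Take 56.5% survival and an event that can arise only after June 2014 and affects 10% of the 334 (33.4 children). To be generous to the fixed analysis, let it occur in June 2014 itself.

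- *Harmless event.* Exposed risk is 23.8 / 334 = 7.1%. Unexposed risk is (215 + 21.4) / (549 - 33.4) = 45.9%. Risk ratio 0.16.
- *Event that doubles later risk.* The unexposed later risk is 23.8 / (300.6 + 2 x 33.4) = 6.5%, so exposed risk is 13.0%. Unexposed risk overall is (215 + 19.5) / 515.6 = 45.5%. Risk ratio 0.29.

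**5. Later events, Cox fits.** These use 400,000 simulated children per cell. Assumed transplant-free survival is 65% or 70% at 1 year, 60.8% (334/549) at 7.5 years, and 50, 56.5 or 60% at 11. Event onset is at a constant rate from 6 months or from 3 years, set so that 5% or 10% of 11-year survivors are affected (the pacemaker range in Section 4.3.1.a).

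| Coding | Harmless event, HR | True HR 2 |
|---|---|---|
| Fixed | 0.04-0.30 | 0.08-0.54 |
| Fixed, onset only after June 2014 | 0.01-0.14 | 0.02-0.26 |
| Time-dependent (5-10% event) | 0.94-1.07 | 1.89-2.07 |

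A separate simulation used 549 children, 215 early endpoints, 24 or 40 later ones, and a harmless late event with 10-30% cumulative risk. Fixed coding gave a median HR of 0.05-0.09 with false rejection in 100% of runs. Time-dependent coding gave 0.86-0.99 with rejection in 3.7-6.0%. The direction under fixed coding was the same in every cell.

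**The case against.** The strongest reply is that the plan never says later events will be fixed covariates. Section 7.1.2.f describes exploration from a pool of candidates shared by several outcomes and does not say every candidate enters the survival model. Cox regression accommodates time-dependent covariates, and Section 7.6 provides for a documented revised plan. This stands: the event bias is conditional on a coding choice that the plan leaves open.

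On SES, Section 4.3.3 already plans the SVR/SVR II data for survival. Complete-case analysis is not specified either, and Section 7.5 requires missing covariates to be reported, so a model stripped of its endpoints would be noticed. That limits the harm, but the stated use of ND-visit SES for survival still cannot work for children who died or were transplanted before the visit.

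A reader might also infer more than the documents support:

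- *That Aim 5 itself offers ND-visit SES as a predictor.* Section 7.1.2.f does not mention SES; the statement is in Section 4.3.3, which does not mention Aim 5.
- *That the 215 children have no medical or surgical history.* Sections 4.3.2.a and 4.3.3 show that earlier histories were collected, so a pacemaker or stroke before an early death may be on record. Only what arose after the last SVR/SVR II contact is confined to later survivors.
- *That event counts or lack of Fontan completion would be distorted by a known amount.* The same mechanism applies, but the documents give neither event rates nor a Fontan completion rate from which to size it.

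**Conclusion.** The concern holds in two limited parts. First, using ND-visit SES to adjust survival at 11 years is unworkable as written: up to 215 of 549 children cannot have a value, and a complete-case model keeps almost no endpoints. This follows from Sections 4.3.3, 5.1 and 5.4; only the exact number kept depends on assumed survival and visit timing.

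Second, the survival risk models lack a rule for later events. If those events were coded as fixed, they would look protective even when they double the hazard. The direction is robust; the hazard ratios depend on the assumed survival curve, event share and onset times, and the survival range is borrowed from a study-end illustration.

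Pre-stage-I and stage I predictors, the randomized shunt comparisons, and the RVEF, exercise and ND models are not materially affected. The documents do not support a claim that the plan commits to a biased method or that its main comparison is compromised. Severity is minor, in an exploratory secondary aim.

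**What to change.** 1. **Section 4.3.3.** Limit survival models to the SES data from SVR and SVR II that the section already plans, and keep ND-visit SES for the ND models.
2. **Section 7.1.2.f and the risk-factor models in Section 7.1.2.b.** State that:
   - risk stratification from randomization uses only predictors known at that time origin;
   - prediction with later events uses landmark models among children still at risk at the landmark;
   - associations of dated later events are estimated with time-dependent covariates, with event frequency as a running count.

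The cost is a few sentences and some extra programming. Event dates are needed; Section 4.3.2.a plans annual histories checked against medical records but does not say that dates are recorded, so this should be confirmed. Late landmark models will have few endpoints: about 24 after June 2014 at 56.5% survival, and roughly 0 to 60 over 50-63%. Power for rare late events will be low. In simulated cohorts of 549 with 7.5% affected, time-dependent coding detected a true hazard ratio of 2 in 20-56%.

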7.2 Number of Subjects to be Enrolled

The proposed study is a prospective observational design of a previously determined, fixed cohort. Out of the 549 subjects randomized in the original SVR trial, 334 subjects are currently alive, free from heart transplant and 331 have single ventricle physiology. Study sample size will depend on the ability to contact families and on the consent rate for contacted subjects.

Conservatively assuming 80% retention of this cohort (N=265) and 10% excluded from the primary measure of RVEF by CMR, either because CMR is not possible due to a pacemaker or because CMR data are not obtainable without general anesthesia or sedation, we anticipate the

primary outcome will be collected and adequate for 239 participants. If there is 90% retention and 10% without CMR, the primary outcome will be obtained in 269 participants.

7.4 Interim Analyses and Stopping Rules for Termination of the Study

As this is an observational study and inclusion of the entire cohort will be valuable, there are no preconceived stopping rules for early termination of the study. However, we would like to reserve the right to look at an interim analysis at some time point such as when all participants have reached 10 years of age (2018). Premature termination of this study may occur because of a regulatory authority decision, or withdrawal of study approval by clinical site IRBs. In addition,

NHLBI retains the right to discontinue the study prior to the inclusion of the intended number of subjects, but intends to exercise these rights only for valid scientific or administrative reasons.

7.5 Spurious Data Procedures

Consistency checks and range checks will be built into the data management system. This will allow many errors to be identified and corrected at the time of data entry. Queries regarding any problems with data will be sent to site coordinators regularly throughout the course of the study. Sites will also be monitored during the study. Therefore, spurious data are expected to be rare. Any data which are judged by the MM to be definitely incorrect, and which cannot be resolved, will be set to missing.

The study report will indicate the number of subjects who have missing data on each study endpoint. For covariate-adjusted analyses, the number of subjects who have missing data on the covariates will be reported.

Throughout the study, the rate, timing, and reasons for subject withdrawal will be monitored by site and treatment arm. Any site with a pattern of differential withdrawal by treatment arm will be queried. If necessary, retraining will take place or the site may be barred from enrolling additional subjects to the study.

7.6 Deviation Reporting Procedures

Any modifications or deviations from the statistical plan described in this protocol will be documented in a "Revised Statistical Plan" document.

7.7 Subjects to be Included in Analyses

All participating subjects will be included in the appropriate analyses, though only participants who have undergone CMR will be included in the analysis for the primary outcome measure of CMR RVEF. The participants who have not had a CMR will be included in analyses related to the secondary outcomes of the primary aim.

8. DATA MANAGEMENT

An Electronic Data Capture (EDC) system will be used for the study that is designed to support reliable and secure data entry for clinical research purposes. The system also provides seamless integration of eCRFs and paper-based CRFs within a single protocol if desired; implementation of protocol amendments; and SAS and XML study data exports.

8.1 Data Entry

Data can be entered directly from multiple study sites via a fully validated and 21 CFR Part 11 compliant, secure Web application and stored centrally. A configurable sample-based double data entry system is available. Data are entered by subject study identification number; names will not be linked with subject data in the database. Study sites will maintain records in secure areas linking the subject name with the identification number assigned for the study. Study sites will have full access to their own data and be able to view these data remotely. Study staff will not be able to view subject data associated with other sites.

8.2 Data Validation and Monitoring

Integrated into the data entry system are real time validations, including both inter- and intra-instrument data checks. Inconsistent or questionable values are flagged during entry, and an edit report is automatically generated to the data entry client. These edit reports provide the information necessary to investigate any data entry errors or resolved questions regarding out-of-range or questionable values. Second level query tracking allows monitors and data managers real time access to unresolved queries as well as the date and time of query generation and resolution.

8.3 Data Security and Integrity

All data changes are written to an audit trail. The audit trail identifies the data item by table, column and key field. The entry includes the user, date and time, as well as the old value and new value. Both patient related data as well as trial configuration data are written to the audit trail. Data are saved at regular intervals during data entry to prevent loss of information in the event of a disruption of the Internet connection. In the unlikely event of a major disruption, a backup connection allows full access to the DMS.

Several levels of security are employed to ensure privacy and integrity of the study data, including the following: Study access requires use of assigned user names and passwords. Individual roles and access levels are assigned by the study data manager. Passwords are changed regularly. Web-based entry uses secure socket layer data encryption. Data will not be stored on laptop computers.

